In vitro studies indicate that ENTO is primarily metabolized by CYP2C9, and to a lesser extent by CYP3A and CYP1A2. Use of nicotine-containing or THC-containing products may induce CYP1A2, which has the potential to affect ENTO metabolism. Due to lower observed ENTO exposure in smokers in Cohort 1, enrollment in Cohort 1 has been expanded to enroll 10 smokers with moderate hepatic impairment (for 8 evaluable) and appropriate matched healthy controls, in order to further investigate the impact of smoking on ENTO PK. To avoid the potentially confounding effect of smoking on the assessment of hepatic impairment on ENTO PK, additional non-smoking subjects with moderate hepatic impairment will also be enrolled in Cohort 1 (10 enrolled for 8 evaluable, and appropriate healthy, matched controls). In Cohorts 2 and 3, only non-smoking subjects with hepatic impairment will be enrolled so that an accurate assessment of the effect of hepatic impairment on ENTO PK can be made, without the potentially confounding effect of smoking.

The trial will enroll subjects with chronically impaired hepatic function and healthy controls, matched for body mass index, age, and sex. This study will proceed in a staggered fashion. Dosing of subjects with mild and/or severe hepatic impairment will occur only after the review of safety and PK from smoking and non-smoking subjects with moderate hepatic impairment. Specifically, Cohort 2 will be initiated if supported by safety and PK findings from subjects in Cohort 1. Cohort 3 will be enrolled if a clinically meaningful change (≥ 2 -fold mean difference from matched healthy controls) in the exposures of ENTO and/or metabolite (if applicable) exposure is identified in non-smoking hepatic impairment subjects in Cohort 1.

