### **Adaptive Cohort 3 (Mild Hepatic Impairment)**

Up to 20 subjects: 10 with mild impairment, up to 10 matched healthy controls, for 8 evaluable subjects per group. Data from healthy subjects in Cohort 1 or 2 who are an appropriate match for a mild impairment subject may be used.

[figure not shown]
Cohort 1 enrollment of hepatic impairment subjects will be an approximate even distribution of subjects who are active cigarette smokers (at least 10 cigarettes/day) and subjects who are current non-smokers (no use of tobacco, nicotine-containing or tetrahydrocannabinol (THC)-containing products within the last 14 days). Hepatic impairment subjects enrolled in adaptive Cohorts 2 and 3 will be current non-smokers (no use of tobacco, nicotine-containing or THC-containing products within the last 14 days).

Designations of hepatic impairment will be assigned as follows:

- Class A (mild): CPT score 5 to 6
- Class B (moderate): CPT score 7-9
- Class C (severe): CPT score 10-15

[figure not shown]
An overview of the study design is shown below in [Figure 1-1](#).

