**Figure 1-2. Study Schema – All Cohorts**

#### **1.4. Sample Size and Power**

Eight evaluable subjects per hepatic function group (for Cohort 1, it is 8 evaluable subjects per hepatic function group within each smoking status group) will provide  $\geq 89\%$  probability for the 90% confidence interval (CI) for the geometric least-squares mean (GLSM) ratio of PK parameters (AUC or  $C_{\max}$ ) for ENTO in the hepatic impairment/dysfunction group(s) versus the appropriate group of matched, healthy controls, to be within limits of 50% to 200%. The calculation assumes an expected ratio of geometric least-squares means of 1.0 in PK parameters and inter-subject standard deviation of 0.455 for the natural logarithm-transformed pharmacokinetic parameters for ENTO. The assumption is based on the data obtained from a prior clinical study of ENTO (Study GS-US-339-0111).

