For subjects hepatic impairment, the relationship between plasma PK exposure parameters  $AUC_{\tau}$  and  $C_{\max}$  and overall CPT impairment score will be explored using Spearman correlation analysis and examined graphically. The relationship between the PK parameters ( $AUC_{\tau}$  and  $C_{\max}$  on Day 5) and baseline lab tests (albumin, total bilirubin, prothrombin time, and International Normalized Ratio [INR]) will be also explored using Spearman correlation analysis and examined graphically for hepatic impaired subjects and for all subjects by hepatic function group.

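### The exploratory correlation of exposure with CPT score does not separate smokers, who are enrolled only at CPT 7-9, so it is biased if only one adaptive cohort opens

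*SAP*

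**What the plan says.** SAP 5.2.2 plans, for impaired subjects, that the relation between AUCtau and Cmax and "overall CPT impairment score will be explored using Spearman correlation analysis and examined graphically". Nothing is said about smoking. The same paragraph plans Spearman correlations of Day 5 exposure with albumin, total bilirubin, prothrombin time and INR, both across impaired subjects and by hepatic function group.

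The other comparisons in SAP 5.2.2 do take account of smoking. In Cohort 1 the ANOVA, the Wilcoxon tests and the protein-binding summary are all split by smoking status.

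The design fixes where smokers sit on the scale. SAP 1.3 states: "Hepatic impairment subjects enrolled in adaptive Cohorts 2 and 3 will be current non-smokers". Impaired smokers therefore exist only in Cohort 1, which is "Class B (moderate): CPT score 7-9". Protocol 1.3 gives the direction of the smoking effect: "Due to lower observed ENTO exposure in smokers in Cohort 1, enrollment in Cohort 1 has been expanded to enroll 10 smokers". For the two adaptive cohorts it explains the restriction as follows: "only non-smoking subjects with hepatic impairment will be enrolled so that an accurate assessment of the effect of hepatic impairment on ENTO PK" is possible.

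**The concern.** A pooled rank correlation cannot tell a severity effect from a smoking effect when smokers occupy only one part of the severity scale. With Cohorts 1 and 2, the low-exposure smokers all lie at the low-CPT end and add an upward trend. With Cohorts 1 and 3, they all lie at the high-CPT end and pull a true upward trend down.

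Both configurations are foreseeable. Protocol 1.3 anticipates that no effect in moderate impairment would make the mild cohort unnecessary, and that a large effect would call for caution about the severe cohort.

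What is at stake is interpretation. This is the planned analysis that treats severity as a graded score, and its result would be reported next to comparisons from which smoking has been removed.

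**Working it through.** The plan gives no figure for this analysis, so there is none to reproduce. The bias was sized by simulation.

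**Inputs from the documents**
- Subjects: "8 evaluable subjects per hepatic function group within each smoking status group" (SAP 1.4). Cohort 1 thus has 8 impaired smokers and 8 impaired non-smokers, and each adaptive cohort adds 8 impaired non-smokers.
- Spread: "inter-subject standard deviation of 0.455 for the natural logarithm-transformed pharmacokinetic parameters for ENTO" (SAP 1.4).
- CPT classes: 5-6, 7-9 and 10-15.

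**Assumptions**
- Smoker/non-smoker geometric mean ratio s = 0.8, 0.7 or 0.5. The documents give only the direction.
- CPT uniform within class, with severe capped at 12.
- Two-sided p < 0.05 for the Spearman test, borrowed from SAP 3.5.

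**Model:** ln(exposure) = slope × CPT + ln(s) × smoker + error, with error SD 0.455; 20,000 trials per setting.

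**Cohorts 1 and 2, no CPT effect (slope 0)**

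| s | Pooled mean rho | Non-smokers only | Significantly positive, pooled (nominal 2.5%) |
|---|---|---|---|
| 0.8 | 0.09 | 0.00 | 6% |
| 0.7 | 0.14 | 0.00 | 9% |
| 0.5 | 0.25 | 0.00 | 19% |

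Repeat runs moved these percentages by a point or two (7% to 21% in one), so they are approximate. The partial Spearman adjusted for smoking also averages 0.00.

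**Cohorts 1 and 3, true gradient**

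Cohort 3 opens only if non-smoking moderate subjects differ at least 2-fold from controls. If controls are placed at CPT 5 on the same line and moderate subjects average CPT 8, a 2-fold effect needs a slope of ln 2 / 3 = 0.231. A slope of 0.1 gives exp(0.3) = 1.35-fold.

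| Slope | Pooled, s = 0.8 | s = 0.7 | s = 0.5 | Non-smokers only |
|---|---|---|---|---|
| 0.231 | 0.50 | 0.45 | 0.30 | 0.58 |
| 0.1 | 0.19 | 0.13 | -0.01 | 0.29 |

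The second row is less likely to be reached. Read as a point-estimate rule, the threshold has standard error 0.455 × √(2/8) = 0.2275. At a slope of 0.1, z = (0.693 - 0.3) / 0.2275 = 1.73, so Cohort 3 opens in about 4% of trials. With no hepatic effect, z = 0.693 / 0.2275 = 3.05, or about 0.1%.

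**Cohort 1 alone.** With no CPT effect, rho is 0.00 for every s. A gradient of 2-fold over 3 points is diluted from about 0.36 to 0.29 at s = 0.5.

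**All three cohorts.** Smokers sit mid-scale, so no correlation is created. At a slope of 0.1, pooled rho is 0.39 to 0.36 (s = 0.7 to 0.5) against 0.46 in non-smokers. Part of that gap is not due to smoking: adding mid-scale subjects narrows the CPT spread. With class effects of 1.25-, 2- and 3-fold, non-smokers give 0.60, and pooling gives 0.52 with no smoking effect at all and 0.47 at s = 0.5.

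**When the sign could flip (Cohorts 1 and 3).** Let m be the moderate/mild exposure ratio in non-smokers. With equal numbers of smokers and non-smokers, the Cohort 1 mean exceeds the mild mean by ln m + 0.5 × ln s. This is negative only if s < 1/m²: s below 0.64 for m = 1.25, 0.50 for m = 1.41 and 0.25 for m = 2.

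**The case against.** The strongest reply is that nothing rests on this analysis. The SAP calls it exploratory, its conclusion rule uses the GLSM ratio, and the Cohort 3 trigger uses non-smokers. SAP 5.2.2 also compares smokers with non-smokers directly among impaired Cohort 1 subjects, so a reader of the report will see the smoking effect. All of this stands and keeps the point small.

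The size is also uncertain. Protocol 1.3 describes the drug as "primarily metabolized by CYP2C9, and to a lesser extent by CYP3A and CYP1A2", and smoking is expected to act through the last of these, so s could be near 1. With 24 subjects the null standard deviation of rho is about 1/√23 = 0.21. A bias of 0.09 to 0.25 is then roughly 0.4 to 1.2 standard deviations: material, but not overwhelming.

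A reader might infer more than the documents support:
- **That pooling generally reverses the correlation.** It needs s < 1/m². With moderate 2-fold, mild 1.6-fold and s = 0.5, mean rho is -0.09 against 0.21 in non-smokers, but only 5% of trials are significantly negative. At the slope that meets the Cohort 3 threshold, the sign stays right.
- **That Cohorts 1 and 3 would show a negative correlation with no hepatic effect.** Cohort 3 would then open in about 0.1% of trials.
- **That the laboratory correlations are affected equally.** The design ties smoking to CPT class, not to laboratory values, and no calculation here covers them. Within the moderate group there is no built-in link.

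Pooling is itself inferred from silence. The SAP does not state it, but it is the natural reading of an analysis defined for impaired subjects with no split.

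**Conclusion.** The point holds as a cheap improvement. As written, the CPT correlation brings back the confounding that the restriction of Cohorts 2 and 3 to non-smokers was meant to avoid, while the main comparisons beside it do not.

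The bias matters only if exactly one adaptive cohort opens. With Cohort 2 alone it is upward, as much as +0.25 in mean rho at s = 0.5. With Cohort 3 alone it is downward: attenuation at a slope consistent with the opening rule, and masking only if the smoking effect is large relative to the gradient. Other configurations give dilution.

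These sizes rest on an assumed smoking ratio, an assumed CPT spread within class and 8 evaluable subjects per cell. The documents support the direction, not the magnitude. No gate, primary comparison or conclusion rule is affected.

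**What to change.** In SAP 5.2.2, state that the CPT-score Spearman correlation will be run either in non-smoking impaired subjects or as a partial Spearman adjusted for smoking status. Show smokers with a separate symbol in the plots. Apply the same to the laboratory correlations that combine all impaired subjects, where bias arises only so far as the laboratory values track CPT class.

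The cost is one WHERE or PARTIAL statement on data already collected. The non-smoker version loses up to 10 subjects, and if only Cohort 1 is enrolled it would leave 8 to 10 subjects on three CPT values. The partial version loses none and is the safer choice if it is not yet known which cohorts will open. SAP section 1 has the plan finalised before the database, so the change belongs there.

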## **6. ANALYSIS OF SAFETY DATA**

Safety data (including AEs, laboratory data, vital signs, safety ECG data, and concomitant medications) will be listed and summarized for subjects in the safety analysis set. All safety data collected on or after the date of the first dose of study drug through to the date of the last dose of study drug plus 30 days will be summarized by hepatic function group within cohort. Data for the pretreatment period will be included in data listings.

A subject's extent of exposure to study drug data will be generated from the study drug administration page in the eCRF. Exposure data will be listed.

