Up to 20 subjects:
10 with severe impairment, up to 10 matched healthy controls if none of the healthy subjects from a previous cohort is an appropriate match for a severe impairment subject, for 8 evaluable per group.

- Adaptive Cohort 3 (CPT Class A, Mild Hepatic Impairment)

[figure not shown]
Up to 20 subjects:

10 subjects with mild impairment, up to 10 matched healthy control subjects if none of the healthy subjects from a previous cohort is an appropriate match for a mild impairment subject, for 8 evaluable per group

The 90% CIs will be examined to determine if a meaningful change (≥ 2 -fold mean difference from matched controls) in the exposures of ENTO and/or metabolite (if applicable) is identified which would be clinically interpreted. A decision to enroll subjects in adaptive Cohort 2 (Severe Hepatic Impairment) and/or adaptive Cohort 3 (Mild Hepatic Impairment) will be enrolled as determined by safety (treatment-emergent AEs, treatment-emergent laboratory abnormalities, vital signs, safety ECGs) and/or PK data from non-smoking moderate hepatic impairment subjects and matching, healthy controls in Cohort 1. Specifically, Cohort 2 will be initiated if supported by safety (treatment-emergent AEs, treatment-emergent laboratory abnormalities, vital signs, safety ECGs) and PK findings from non-smoking subjects and healthy, matched controls in Cohort 1. Cohort 3 will be enrolled if a clinically meaningful change (≥ 2 -fold mean difference from matched healthy controls) in the exposures of ENTO and/or metabolite (if applicable) exposure is identified in non-smoking hepatic impairment subjects in Cohort 1..

[figure not shown]
An overview of the study design is shown below in [Figure 3-1](#)

Figure 3-1. High Level Study Schema

The study schema for all subjects is shown in [Figure 3-2](#)

Figure 3-2. Study Schema – All Cohorts

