### **4.2. Baseline Characteristics**

#### **4.2.1. Demographics and Baseline Characteristics**

Subject demographic data (age, sex, race, and ethnicity), baseline characteristics (CPT score, body weight, height, and BMI), and estimated glomerular filtration rate (eGFR) by Cockcroft-Gault (CG) method will be summarized using descriptive statistics for the safety analysis set. Eight summary statistics (sample size, mean, standard deviation, median, Q1, Q3, minimum, and

maximum) will be presented for continuous data (age, weight, height, BMI, and eGFR). Age (in years) will be calculated from the date of first study drug dosing if dosed, enrollment if not dosed. The number and percentage will be presented for categorical data (sex, race, ethnicity, and CPT Score). Additionally, body weight, height and BMI will be summarized for males and females separately. Note that the summary of demographics and baseline characteristics will be provided by hepatic function group and smoking status within cohort.

In addition to the summary tables, a listing will be provided for all demographics and baseline characteristics data.

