### **6.1.8. Summaries of Adverse Events**

In summary tables, SOC will be presented alphabetically and events within SOC will be presented by decreasing frequency count, based on the total number of events by hepatic function group. For each SOC and PT, the number and percentage of subjects reporting an event will be calculated by hepatic function group.

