### **6.2.2. Summaries of Laboratory Results**

Chemistry and hematology laboratory tests will be summarized by hepatic function group using descriptive statistics (sample size, mean, SD, median, Q1, Q3, minimum, and maximum) for predose assessments, postdose assessments, and change from predose assessments.

In the case of multiple values in an analysis window, data will be selected for analysis as described in Section 3.8.3. See Section 3.6 for details on missing data, and see Section 3.8 for details on analysis windows for these data.

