### **6.2.5. Summaries of Graded Laboratory Abnormalities**

The incidence of treatment-emergent graded laboratory abnormalities (number and percentage of subjects) will be presented by hepatic function group. Only the maximum postdose abnormality grade (by each laboratory test or overall as appropriate) observed will be counted. The denominator is the number of subjects with non-missing postdose values in the given analysis window.

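### Cohort 1 safety tables pool smokers with non-smokers, so the moderate-impairment column is not like-for-like with the non-smoking controls or with impaired subjects in Cohorts 2 and 3

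*SAP*

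**What the plan says.** SAP section 6 sets the general rule that safety data through the last dose "plus 30 days will be summarized by hepatic function group within cohort". The subsections follow it:

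- SAP 6.1.8, adverse events: "the number and percentage of subjects reporting an event will be calculated by hepatic function group".
- SAP 6.2.2, laboratory values: "Chemistry and hematology laboratory tests will be summarized by hepatic function group using descriptive statistics".
- SAP 6.2.5, graded abnormalities: "The incidence of treatment-emergent graded laboratory abnormalities (number and percentage of subjects) will be presented by hepatic function group".
- SAP 6.3 (vital signs) and 6.4 (ECG) also use hepatic function group. The ECG table adds only the predose result.

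Nothing in SAP section 6 mentions smoking. Elsewhere the SAP does use it. Demographics are "provided by hepatic function group and smoking status within cohort" (SAP 4.2.1). PK parameter summaries (5.2), and PK comparisons and protein binding (5.2.2), are also split by smoking status in Cohort 1.

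The protocol gives the reason for that split. Section 1.3 says Cohort 1 was enlarged "Due to lower observed ENTO exposure in smokers in Cohort 1", and it restricts Cohorts 2 and 3 to non-smoking impaired subjects so that smoking does not confound the effect of impairment on PK. The statistical methods in the synopsis nevertheless group safety by hepatic function only.

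**The concern.** Incidences of adverse events and of laboratory abnormalities are the study's secondary endpoints. For moderate impairment, the planned tables report each as one average over two subgroups that the trial enrols separately because their exposure differs. The columns a reader will set beside it are the controls and, if those cohorts open, mild and severe impairment. None of these contains smokers. A difference between columns, or the lack of one, could then reflect hepatic function, smoking or both, and the tables would not help to separate them.

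The documents also describe one safety effect with an exposure-related mechanism. Protocol 1.2.3 expects transient rises in indirect bilirubin through UGT1A1 inhibition. If these are less frequent at the lower exposure in smokers, a pooled rate understates what occurs at non-smoker exposure.

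**Working it through.** The documents state no safety rate or precision, so there is no planned figure to reproduce. Their one probability statement (SAP 1.4) concerns PK confidence intervals and is not used here.

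**Step 1: smoking mix of each column, by design**

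| Column | Source | Smokers |
|---|---|---|
| Moderate impairment, Cohort 1 | SAP 1.3: 10 smokers and 10 non-smokers | 10/20 = 50% |
| Healthy controls | Protocol 4.3.3: no nicotine from 14 days before dosing through follow-up | 0% |
| Severe impairment, Cohort 2 | Protocol 1.3 and 4.2.2; SAP 1.3: 10 planned | 0/10 = 0% |
| Mild impairment, Cohort 3 | same | 0/10 = 0% |

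The imbalance against controls exists within Cohort 1 alone. The imbalance against mild and severe impairment arises only if Cohorts 2 and 3 enrol.

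**Step 2: effect on an event rate**

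Let p be the event rate in non-smokers, and let k be the ratio of the smoker rate to the non-smoker rate. With 10 subjects in each:

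pooled rate = (10p + 10kp)/20 = p(1 + k)/2

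The documents do not give k, so a range is assumed that covers both directions. The example column assumes p = 40%.

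| k (assumed) | Pooled as share of non-smoker rate | Pooled rate when p = 40% |
|---|---|---|
| 0 | 50% | 20% |
| 0.25 | 62.5% | 25% |
| 0.5 | 75% | 30% |
| 0.75 | 87.5% | 35% |
| 1 | 100% | 40% |
| 1.5 | 125% | 50% |

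**Step 3: effect on average exposure**

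Protocol 1.3 reports lower exposure in smokers but no size. Let r be the ratio of smoker to non-smoker exposure. A 10:10 pooled geometric mean is then √r of the non-smoker value. For assumed r of 0.3, 0.5 and 0.7, it is 55%, 71% and 84%.

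**Step 4: precision after the split**

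Exact 95% intervals: 4 events in 10 subjects gives 12% to 74%; 4 in 20 gives 6% to 44%; 5 in 20 gives 9% to 49%. The split columns are imprecise, but their size matches the 10 subjects planned for each impaired group in Cohorts 2 and 3.

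**The case against.** The case for leaving the tables alone has real force.

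- **The SAP follows the protocol.** The synopsis groups safety by hepatic function, and the smoking objective concerns PK only. This stands: the gap is shared by both documents, and the SAP does not depart from the protocol.
- **The direction is not established.** A reader might infer that pooling makes moderate impairment look safer than it is. The documents do not support that. They give neither the size of the exposure difference nor an exposure-event relation at 100 mg twice daily, and they report much higher doses as well tolerated in healthy subjects. Smoking itself could raise some event rates. The bilirubin mechanism makes dilution plausible for that kind of abnormality, but no more.
- **No formal safety comparison across severity is planned.** Summaries are organised within cohort, and SAP 6.2.1 rules out inferential statistics for laboratory data. This stands. The issue is what a reader can take from descriptive columns set side by side.
- **The cohort decision does not rest on these tables.** A reader might infer that the SAP fails to supply the table needed to open Cohort 2, because Protocol 3.1 relies on safety and "PK findings from non-smoking subjects and healthy, matched controls in Cohort 1". But the SAP governs the clinical study report, while that decision is taken during the study. The protocol is also not uniform on which subjects inform it.
- **Listings by subject are planned.** The split could therefore be rebuilt by hand. However, the vital sign and ECG listings (SAP 6.3 and 6.4) name cohort and hepatic function group, not smoking status.
- **The grouping phrase may be shorthand.** SAP 5.2.1 omits smoking under a parent section that includes it. Nothing in section 6 signals the same intent.

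Splitting the controls by matched stratum separates no smoking exposure, because no control may smoke.

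**Conclusion.** The point holds as one of comparability. The planned moderate-impairment safety column is about 50% smokers. The controls, and the impaired subjects in Cohorts 2 and 3 if they enrol, are 0% smokers. That follows from the design and needs no assumption about event rates.

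Dilution of exposure-related events is possible but unproven. Over assumed event ratios of 0 to 1.5, the pooled rate runs from 50% to 125% of the non-smoker rate, with no distortion at a ratio of 1. The arithmetic assumes equal numbers of smokers and non-smokers, as planned.

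The change is worth making because it uses a stratum the trial already enrols by and already applies to demographics and PK. It concerns the presentation of secondary endpoints. It does not affect the primary PK analysis.

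**What to change.** 1. In SAP 6, 6.1.8, 6.2.2, 6.2.5, 6.3 and 6.4, present Cohort 1 moderate impairment as non-smokers, smokers and total. Showing controls by matched stratum is optional.
2. State that any descriptive comparison of moderate impairment with Cohort 2 or 3 uses the non-smoker column.
3. Add smoking status to the grouping in SAP 5.2.1, so that it agrees with SAP 5.2 and Protocol 8.6.
4. Separately, reconcile the protocol passages on which Cohort 1 subjects inform the decision on later cohorts. The synopsis under Number of Subjects Planned bases the start of Cohort 2 on Cohort 1 subjects generally. So does section 1.3, which also requires review of both smokers and non-smokers. The synopsis under Study Procedures, section 3.1 and section 5.3 refer to non-smokers and their matched controls. The SAP should not settle this by naming a table column.

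Items 1 to 3 need only SAP wording and extra table columns, with no new data and no protocol amendment. The price is denominators of about 10 per column, where one event moves a rate by 10 percentage points; keeping the total column limits that loss. Item 4 is a protocol clarification.
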